- for social workers and family support workers: the social worker or family support worker was a member of a team assigned to the intervention at point of randomisation and 0 else;
- for foster / kinship carers: the carer cares for a child or young person whose case is held at the point the foster carer enters the sample, by a social worker who is a member of a team assigned to the intervention at point of randomisation and 0 otherwise.

Although there is some turnover of social workers, family support workers and foster carers, about 80% of those at T0 (April 2021) will still be working with the local authority at T13 (May 2022), and so 80% will have received the full 12 months of the intervention. Binarising the treatment seems a reasonable proxy in this case.

For the outcomes relating to children, treatment is coded as a binary variable. When children enter the sample, at either the point of randomisation, or the point they become eligible (e.g. their case opens and meets other criteria) they will be allocated to treatment if the team of their allocated social worker was randomised to treatment.

Covariates

Including control variables increases the precision of the estimate. In each regression, we control for a number of relevant covariates. We outline different categories of covariates below.

Site effects

We include site fixed effects but not site-treatment interaction terms.

Previous outcome measures

We control for the previous measurements of the outcome variable where data is available. For the survey-based measures for social workers, family support workers and foster carers, the same measures will be asked at T6 (October 2021) and T13 (May 2022), and for administrative data we expect previous values to be available. For the outcomes of the CYP and parents / carers (including kinship carers), the previous measure of the outcome will be at T0 (April 2021) or when they entered services if they entered services after T0 (April 2021).

Other covariates

For CYP outcomes (primary outcome i) and secondary outcome i)), we include the following vector of individual-level covariates:

- gender (coded as male, female, or other/missing)
- age group (4-11, 12-17, 18 years, or missing with 4-11 as the reference category)
- ethnicity (Asian / Asian British, Black / African / Caribbean / Black British, Mixed / Multiple ethnic groups, Other ethnic group, White, missing; with the majority group as the reference category)

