Although the total intervention period lasts for 12 months, children and young people enter and leave services throughout the year with an estimated 50% of children and young people at T0 having left services by T13. Because of the extent of the dropoff and because an insight into the impact of the number of sessions Kitbags are used may affect future planning of how Kitbags are used in direct work, we considered it important to analyse the “dosage” of the treatment (where number of months of exposure is taken as a proxy of the number of sessions). Thus for CYPs’ and parents’ / carers’ outcomes (which are collected at the same time as the child’s), we have four possible “dosages” of the treatment: 0 months (control), 0-4 months, 4-8 months and 8-12 months. We test whether the programme affects the duration of the interaction with children’s social care (end date - start date) by regressing the duration of interaction with children’s social care on the independent variables defined in the regression specification above. If the coefficient on the treatment dummy is insignificant, we can be less concerned that the impact of the treatment is determining dosage and we code the treatment variable for the children and young people’s outcomes and the parent / carers’ outcomes as categorical:

- 0: control
- 1: 0-4 months’ treatment
- 2: 4-8 months’ treatment
- 3: 8-12 months’ treatment

The control condition (coded as 0) will be the base category, and so the coefficient on each of the dosages of the treatment can be interpreted as the impact of 0-4 months / 4-8 months / 8-12 months of the treatment on the outcome compared to control.

Dosage will only be tested for child and parent / carer outcomes as the dosage is likely to vary much for them than social workers and family support workers:

$$Y_{ict13} = \beta_0 + \beta_{1:3} D_c' + \beta_{4:6} A_c' + \beta_7 Y_{ict0} + \beta_{7:k+7} X_i' + \epsilon_c$$

Where:

- D_c is a vector of treatment dosages
- And all else is defined as above

Impact on CYP with different levels of CSC involvement

It may be that there is a differential impact for CYP depending on the type / extent of social care involvement (if the child is on a child in need plan or a child protection plan or whether they are looked after). We add an interaction term of treatment and most recent type of CSC intervention at the start of the intervention period:

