 - the social worker or family support worker is a member of a team assigned to the intervention group,
 - foster carer cares for a child or young person who case is held by a social worker who is a member of a team assigned to the intervention group, or
 - the child or young person's case is held by a social worker in a team assigned to the intervention group.
- I'_i is a vector of interaction terms between the treatment (binarised) and age group (4-11, 11-17, 18 years, or missing with 4-11 as the reference category)
- All other variables are the same as the regression specification outlined under the "Primary and Secondary Analysis" section.

These are exploratory because the analysis was not designed to be sufficiently powered for subgroup analysis.

Contextual Factors Analysis

Where caseloads are high and complex, we would expect that there is less time for direct work. Ideally, we would be able to track the caseload and complexity of each social worker but caseload numbers may have different definitions in each local authority and case complexity is not routinely recorded. We thus ask social workers' for their subjective judgement of their caseload and case complexity over the last year in the social worker survey at T13. We multiply the responses to these two questions to get a proxy for workload (a continuous variable).

We add an interaction term of treatment and workload:

$$Y_{ict13} = \beta_0 + \beta_1 D_c + \beta_{2:4} A_c' + \beta_5 Y_{ict0} + \beta_6 I_i + \beta_{7:k+7} X'_i + \epsilon_c$$

Where:

- D_c is a binary treatment variable for all participant groups to conserve power. Where treatment = 0 if they are in the comparator group and treatment = 1 if:
 - the social worker or family support worker is a member of a team assigned to the intervention group,
 - foster carer cares for a child or young person who case is held by a social worker who is a member of a team assigned to the intervention group, or
 - the child or young person's case is held by a social worker in a team assigned to the intervention group.
- I_i is an interaction term between the treatment (binarised) and workload
- All other variables are the same as the regression specification outlined under the "Primary and Secondary Analysis" section.

Missing data strategy

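### The exploratory dosage and workload models let duration and workload act only in the treated arm, so their coefficients mix ordinary differences with any Kitbag effect

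*Protocol*

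**What the plan says.** **Dosage (Protocol, Exploratory Analysis, Dosage).** For child and parent/carer outcomes, "we have four possible “dosages” of the treatment: 0 months (control), 0-4 months, 4-8 months and 8-12 months". "The control condition (coded as 0) will be the base category", and "the coefficient on each of the dosages of the treatment can be interpreted as the impact of 0-4 months", with the same reading for the two longer bands. Months of exposure stand in for number of sessions, and the section says the result may inform how Kitbags are used in future. The motive is turnover: "an estimated 50% of children and young people at T0 having left services by T13".

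One safeguard is given. Duration of social care involvement is first regressed on treatment and the covariates: "If the coefficient on the treatment dummy is insignificant, we can be less concerned that the impact of the treatment is determining dosage". The dosage coding then goes ahead.

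Duration appears neither in the dosage equation nor in the list introduced by "we include the following vector of individual-level covariates" (Analysis plan, Covariates).

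**Workload (Protocol, Contextual Factors Analysis).** Two T13 survey answers are multiplied into a workload score. The term added to the model "is an interaction term between the treatment (binarised) and workload". All other variables are those of the main specification, whose covariate lists contain no workload term.

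**The concern.** In both models a factor that can be observed in both arms (duration, workload) may shift the outcome only among the treated. Whatever ordinary relation the factor has with the outcome is then loaded onto a treatment coefficient.

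For dosage, a treated child with a short stay is compared with all controls, short and long stays together, rather than with controls who also had short stays. For the status outcome this is severe, because leaving services is part of what the outcome scores. The safeguard asks a different question: whether treatment changes duration. The fault is present in full when duration is distributed identically in the two arms.

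At stake is a dose-response statement, presented as impact, that could guide how many months of Kitbag use are thought worthwhile.

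**Working it through.** The Protocol gives no figure for either model. Its one computed design figure, the MDES of 0.127, concerns the main comparison. The standard formula with the stated inputs gives 0.124, and nothing below depends on it.

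**1. What the dosage coefficients estimate with no effect.** Let m_k be the mean outcome in duration band k (the same in both arms) and p_k the share of children in it. Covariates aside, the expected coefficient is

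b_k = m_k - (p_1 m_1 + p_2 m_2 + p_3 m_3).

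This is zero in every band only if outcome is unrelated to duration. Also p_1 b_1 + p_2 b_2 + p_3 b_3 = 0, so if the coefficients are not all zero, at least one is negative and at least one positive.

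**2. Why the status outcome is linked mechanically.** Outcome measures lists case closure as a level and scores each downward step -1. Under Participants, cases must start before December 2021 and evaluation ends in May 2022, so every child has about 5 months or more available. A child with 0-4 months has therefore normally left services early, which counts as de-escalation.

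**3. Illustrative size, status outcome.** Take the Protocol's 50% leaving. Assume that leavers exit evenly over 12 months and drop one step (-1), and that stayers score 0.

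- Mean of all controls: 0.5 × (-1) = -0.50.
- 0-4 months (share 1/6, all leavers): -1 - (-0.50) = -0.50.
- 4-8 months (share 1/6, all leavers): -1 - (-0.50) = -0.50.
- 8-12 months (share 2/3, of which 1/6 leavers): -(1/6)/(2/3) = -0.25, so -0.25 - (-0.50) = +0.25.

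A simulation of this case (60 teams of 150, ICC 0.03, team-clustered errors, 400 runs, no effect) gave -0.50, -0.50 and +0.25, each significant in 100% of runs. The duration pre-test was significant in 4%. A second null simulation, with monthly status transitions and about half of cases ending within 12 months, gave -0.67, -0.10 and +0.19, significant in 100%, 98% and 100% of runs; the pre-test passed in about 95%.

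**4. Illustrative size, generic association.** With the same exit pattern, mean duration is 0.5 × 12 + 0.5 × 6 = 9 months and its variance is 96 - 81 = 15 (SD 3.87). The 0-4 month band averages 2 months, which is (2 - 9)/3.87 = -1.81 SD from the mean.

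| Association (SD per SD of duration) | 0-4 month coefficient (SD) | Falsely significant |
|---|---|---|
| 0.05 | -0.09 | 36% |
| 0.1 | -0.18 | 88% |
| 0.2 | -0.36 | 100% |

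**5. Same data, bands entered in both arms with treatment interactions.** The treated-control differences averaged zero to within 0.003 and rejected in 2-8% of runs.

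**6. Workload.** Suppose the outcome rises g SD per SD of workload in both arms, with no treatment effect. The written model holds the control slope at zero, so the interaction takes the whole slope g and the treatment coefficient becomes -g × mean/SD of workload. The answer scale is not stated. With two uniform 1-5 answers the product has mean 9 and SD √(121 - 81) = 6.32, so g = 0.1, 0.2, 0.3 gives -0.14, -0.28, -0.43. Simulation gave -0.14, -0.29, -0.43.

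False significance of the interaction follows. About 600 staff is an assumption, twice the 300 intervention staff in Table 2; about 60 is the 10% response in the Data collection schedule.

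| Slope (SD) | About 60 respondents | About 600 |
|---|---|---|
| 0.1 | 13-14% | 42% |
| 0.2 | 24-27% | 94% |
| 0.3 | 38-42% | 100% |
| 0.4 | 65-67% | not run |

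At 60 respondents the test rejects in about 8% of runs even with no slope. With the main effect added, rejection was 4.5-7% at about 600 and about 8% at about 60.

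**The case against.** - **The analyses are exploratory.** This stands as a limit on consequence. It excuses low power, but not a stated reading that is wrong in expectation. The carer comparison among looked-after children is labelled non-causal in the Protocol; the dosage section carries no such label.
- **Closure is not part of every outcome.** This stands. SDQ is limited to children looked after continuously for 12 months or more with at least four months of Kitbag use, so its 0-4 month band should be empty. Carer self-efficacy does not score closure either. For these outcomes only ordinary confounding by duration is in question.
- **Short duration does not always mean closure.** This stands for the 4-8 month band: a child entering in late 2021 can be there with an open case in May 2022.
- **The workload main effect may have been meant.** This is possible, since the equations are loosely written. But neither the equation nor the covariate lists contain it, whereas the model by level of social care involvement states that its moderator is among the covariates.
- **Potential exposure answers another question.** This stands: it measures time since entry, not sessions received. The simulated correction used realised bands in both arms, not potential exposure.

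**Conclusion.** Both models are wrong as written. The dosage coefficients cannot be read as the impact of a number of months, and the pre-test does not rescue that reading. This follows from the coding alone. The sizes do not: they rest on assumed exit patterns and associations. For the status outcome, null simulations gave about -0.5 to -0.7 steps at 0-4 months, -0.1 to -0.5 at 4-8 and +0.2 to +0.25 at 8-12, where negative is the favourable direction. The workload interaction is exposed to a degree that depends on the unknown slope and response.

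Three stronger readings are not supported:

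- A reader might infer that the trial's main results are biased. They are not: the primary and secondary analyses use binary intention-to-treat coding, and the cost valuation uses that treatment coefficient.
- A reader might infer that the dosage model is bound to show a large benefit at short exposure and harm at long exposure. The Protocol gives no transition rates from which to say so.
- A reader might infer that all the interaction models share the workload fault. The model by level of social care involvement carries its main effect, and age group is already a covariate.

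**What to change.** 1. **Dosage.** Define exposure categories in both arms, fit category main effects plus treatment × category, and report the treated-control difference within each category. For the status outcome, use potential exposure (entry date to end of evaluation), which is fixed at entry, in place of realised duration. If realised duration is kept for other outcomes, enter it in both arms and label the result non-causal, because it is observed after randomisation. Remove the sentence that reads the coefficients as impact.
2. **Workload.** Add the centred workload main effect, and label the result associational because workload is measured at T13.

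**Cost.** No new data are needed: the duration regression already requires start dates, and the survey goes to both arms. The price is in the question answered. Potential exposure measures time since entry rather than sessions, its range narrows to about 5-12 months, the 0-4 month category disappears, and all cases open at T0 fall in the top category. The Protocol should state these limits.

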There has been no additional adaptation of the Kitbag itself from the school setting but the support is tailored to the social work setting, focusing on the relationship-based and reflective practice skills of the social workers and their role in leading the shift in practice within their teams.

As mentioned above, we expect that the version of the programme trialled will involve considerably more use of the Kitbag Online than in non-Covid-19 times. We attempt to address the generalisability of the findings in the implementation and process evaluation (please see below).

Logic model

* indicates outcomes that will be measured.

Impact Evaluation

Research questions

Primary research questions

Child outcomes:

- Primary outcome 1: What is the impact of the “Putting the Kitbags to work” programme on the number of **escalations and de-escalations** of eligible children supported by social workers? The comparison is between eligible children supported by social workers in teams randomly allocated to the intervention arm compared with eligible children supported by social workers in teams randomly allocated to the control arm within the intervention period.
- Secondary outcome 1: What is the impact of the “Putting the Kitbags to work” programme on the **behaviour** of eligible children supported by social workers? The comparison is between eligible children supported by social workers in teams randomly allocated to the intervention arm compared with eligible children supported by social workers in teams randomly allocated to the control arm. The outcome will be measured by the total difficulties score of the Strengths and Difficulties Questionnaire. The population will be restricted to children who’ve been looked after continuously for 12 months or more whose SDQ has been assessed from T4 - T12.

Social worker outcomes:

[figure not shown]
- Secondary outcome 2: What is the impact of the “Putting the Kitbags to work” programme on the **self-efficacy** (as measured by the competency subscale of the Work-Related Basic Needs Satisfaction scale) of social workers and family support workers in teams randomly allocated to the intervention arm compared with social workers and family support workers in teams randomly allocated to the control arm? The outcome will be measured at month 6 and month 13 after intervention began.

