MDES was determined by the Excel macro PowerUp⁸ for a 3-level fixed effects blocked cluster random assignment design with treatment at level 2 (BCRA3_2f). The three levels are individual (as we're detecting power for the primary outcome this is the child / young person), social worker team and local authority with treatment assigned at the social worker team level to 50% of the teams. One would not expect high intraclass correlation within teams themselves

⁸ Dong, N. and Maynard, R. A. (2013). *PowerUp!*: A tool for calculating minimum detectable effect sizes and sample size requirements for experimental and quasi-experimental designs. *Journal of Research on Educational Effectiveness*, 6(1), 24-67. doi: 10.1080/19345747.2012.673143

as cases aren't assigned to a team on the basis of similarity other than the level of social work involvement (child in need, child protection etc) (0.03). Baseline is expected to be highly predictive of endline SDQ score (0.8).

Outcome measures

The aim of Kitbag is to improve children's emotional literacy and ability to understand, express and regulate their emotions as well as improving their behaviour and relationships with others. The primary outcome measure is emotional and behavioural difficulties. The other outcomes are secondary outcomes.

Primary Outcomes

Child Outcomes

1i) Children's social care involvement

Given that we may have concerns about selection bias into the primary data collection, we shall also estimate the impact of the Kitbag programme on administrative outcomes which can be collected for all children and young people in the eligible population. Although children's social care administrative outcomes are more tangentially related to Kitbag and are also more difficult to change in a relatively light touch intervention, they have the benefit of not being subject to attrition bias. Kitbag will be delivered to children and young people with all levels of social work involvement, and the logic model does not suggest that it will be particularly beneficial for children and young people with particular children's social care profiles. The third secondary outcome measure is the level of children's social care involvement (2iii). Specifically, this is operationalised as the sum of escalations and de-escalations over the course of the intervention (May 2021 - May 2022):

- case closed
- child on child in need plan
- child on child protection plan
- child in care

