We measure this outcome through a decrease in the total difficulties score of the SDQ (the sum of the emotional, peer, behavioral and hyperactivity subscales - all except the prosocial score as scored according to the instructions by the SDQ developers¹⁴). The score ranges from 0 to 40 with a lower score representing better behaviour. Although the individual subscales appear to measure distinct concepts in high total difficulty score populations (like children with a social worker)¹⁵, we use the total difficulty score instead of the individual subscales to reduce measurement error.

For this outcome, the population is restricted to children who've been i) continuously looked after for 12 months or more and ii) who have used Kitbag for four months or more at the time of their SDQ being assessed. i) is the population for whom SDQs are available in administrative datasets and we further restrict this population to ii) to allow for the minimum number of uses of the Kitbag.

Social Worker and Family Support Worker Outcomes

2ii) Social worker / family support worker self efficacy

As represented in the logic model, one of the hypothesised mechanisms is that social workers feel they have the tools to do their job well. We shall measure whether Kitbag improves social workers' self-efficacy through the competence subscale of the Work-Related Basic Needs Satisfaction scale. The competency subscale is a 4-item scale which respondents agree or disagree on a 5-point Likert scale with good reliability (a Cronbach's alpha of .85), and reasonable predictive validity (correlates positively with job satisfaction and vigour, and negatively with exhaustion)¹⁶. The fourth secondary outcome measure is the mean of the responses for the 4 items where "totally disagree" is coded as 1 and "totally agree" is coded as 5 (2iv).

2iii) Stress

As represented in the logic model, one of the hypothesised mechanisms is that social workers feel more valued by the local authority and feel better supported by their team, reducing their stress. Social worker stress will be measured by the 7-item "Stress in General" scale which has good reliability (above 0.7) and good convergent validity (it correlates negatively as expected with job satisfaction and positively with intention to quit)¹⁷. Higher scores represent

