$$Y_{ict13} = \beta_0 + \beta_1 D_c + \beta_{2:4} A_c' + \beta_5 Y_{ict0} + \beta_{6:9} I_i' + \beta_{10:k+10} X_i' + \epsilon_c$$

Where:

- D_c is a binary treatment variable for all participant groups to conserve power. Where treatment = 0 if they are in the comparator group and treatment = 1 if:
 - the social worker or family support worker is a member of a team assigned to treatment,
 - foster carer cares for a child or young person who case is held by a social worker who is a member of a team assigned to the intervention group, or
 - the child or young person's case is held by a social worker in a team assigned to the intervention group.
- I'_i is a vector of interaction terms between treatment (again binarised) and the categories of the most recent type of CSC intervention (coded as Child in Need, Child Protection Plan, or Looked After - LA fostering / kinship care, Looked After - IFA / other LA fostering / other placement type, or missing; with Child in Need as the reference category).
- X'_i is a vector of covariates including the most recent type of CSC intervention.
- All other variables are the same as the regression specification (depending on the outcome under consideration) outlined under the "Primary and Secondary Analysis" section.

We interpret the coefficient on each interaction term as the differential impact of Kitbags on each cohort in comparison with CYP with a CINP. Whether there is a differential impact by CSC involvement may be related to a few factors: whether Kitbags are more helpful for a particular cohort, whether Kitbags are used differently with different cohorts or whether Kitbags are used at different frequencies with different cohorts. This trial of Kitbags where social workers use Kitbags on their visits is the intervention developer's current best guess about the way that social workers would use Kitbags if the programme were to be rolled out more generally. Given this, it isn't necessarily problematic that the coefficient estimates on the interaction terms encompass these reasons why the treatment may be different for different cohorts. However, it is helpful for the future development of the intervention to try to pick apart these.

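### For the SDQ outcome, the exploratory treatment-by-status model is not estimable with Child in Need as reference, because SDQ children were all already in care at the start

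*Protocol*

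**What the plan says.** Under Exploratory Analysis, in the section on impact by level of CSC involvement, the Protocol writes: "We add an interaction term of treatment and most recent type of CSC intervention at the start of the intervention period". Status has five categories: Child in Need (the reference), Child Protection Plan, looked after in local-authority fostering or kinship care, looked after in independent-agency (IFA), other-authority or other placements, and missing. The equation therefore carries four interaction terms, and the stated reading is: "We interpret the coefficient on each interaction term as the differential impact of Kitbags on each cohort in comparison with CYP with a CINP". The other variables follow the main specification "depending on the outcome under consideration".

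The same section goes on to read the treatment-by-Child-Protection term, and treats the treatment-by-IFA/other term as perhaps the better guide to impact on looked-after children. It then refits with IFA/other as the reference and reads the fostering/kinship interaction against that group.

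The SDQ population is narrower. Under Research questions, secondary outcome 1 is restricted to children "looked after continuously for 12 months or more whose SDQ has been assessed from T4 - T12". Section 2i repeats the restriction ("continuously looked after for 12 months or more") and explains that this "is the population for whom SDQs are available in administrative datasets". The Other covariates section puts the primary outcome and the SDQ together as the two CYP outcomes that share one covariate list, which includes the status variable.

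**The concern.** An interaction model with a reference category needs children in that category. The SDQ restriction appears to remove them: a child with 12 months in care at an SDQ dated no later than T12 should already have been in care when status is recorded. If so, the Child in Need reference cell is empty for this outcome and the coefficients the section undertakes to interpret do not exist.

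The practical risk is that regression software commonly deletes redundant columns and still prints a table. A reader applying the stated rule would take the surviving terms as differences from Child in Need children, when no such child has an SDQ in the analysis. The plan would also seem able to say whether behaviour effects differ between Child in Need, Child Protection and looked-after children, which this SDQ sample cannot show.

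**Working it through.** **Does the model cover the SDQ?** The section names no outcome. It takes its remaining terms from the main specification according to the outcome, and the covariate section lists two CYP outcomes, one of them the SDQ. Nothing in the section excludes or adapts for the SDQ.

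**Dates.** The treatment-variable section gives T0 = April 2021 and T13 = May 2022. Hence T1 = May 2021, T4 = August 2021 and T12 = April 2022. Section 1i starts the intervention period in May 2021. Counting the 12 months back from the SDQ date:

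- SDQ at T4: in care since T4 − 12 = T−8 (August 2020) or earlier.
- SDQ at T12: in care since T12 − 12 = T0 (April 2021) or earlier.

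Even the latest SDQ implies care before T1. At the start, every SDQ child is looked after, or has missing status. Child in Need and Child Protection are empty.

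**Identification.** Write D for treatment and P, L, F, M for the Child Protection, fostering/kinship, IFA/other and missing indicators. The relevant part of the model is

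a + bD + γP·P + γL·L + γF·F + γM·M + δP·DP + δL·DL + δF·DF + δM·DM,

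which has 2 + 4 + 4 = 10 columns. In the SDQ sample:

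- P = 0 and DP = 0 for every child, so δP has no data.
- L + F + M = 1, so the status indicators sum to the intercept.
- DL + DF + DM = D, so the interactions sum to the treatment column.

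Adding any constant k to b and subtracting it from δL, δF and δM leaves every fitted value unchanged. So b and these interactions are not identified. What remains identified is b + δL, b + δF and their difference δL − δF: the effect in each looked-after group and the contrast between them.

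**Rank.**

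| Sample | Independent columns | Rank of 10 |
|---|---|---|
| SDQ, no missing status | L, F, DL, DF | 4 |
| SDQ, some missing status | L, F, M, DL, DF, DM | 6 |

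A numerical check added three site indicators and the baseline score (14 columns), using simulated data with 60 teams, 1,500 children and assumed status shares. Ranks were 8 of 14 with no missing status and 10 of 14 with an assumed 5% missing, that is 4 + 4 and 6 + 4. In both cases D and all four interactions were not estimable. With all five statuses present, as for the primary outcome, the rank was 14 of 14. The rank depends only on which cells are empty, not on the assumed shares.

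**What software would print.** If DF is dropped, the coefficient on D is the effect in the IFA/other group and the one on DL is fostering/kinship minus IFA/other. If D itself is dropped, each interaction is the whole effect in its group. In neither case is any term a difference from Child in Need children.

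**Refit with IFA/other as reference.** D and the fostering/kinship interaction are both estimable. Only the terms of empty categories fall out.

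**The case against.** The strongest reply is that the section already contains the remedy. Its second fit uses IFA/other as the reference and so identifies the one contrast between named groups that the SDQ can support. This stands: a reader might infer that every interaction in the section is read against Child in Need, and that is not so.

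A reader might also infer that the Protocol will report a behaviour effect in Child in Need children. The text does not say this. The quoted rule interprets interaction terms only, the main treatment coefficient is never labelled a Child in Need effect, and an analyst may well notice the empty cells.

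It is also fair that application to the SDQ is implied and not stated. The site-effects section says explicitly that it covers all outcomes; this one does not.

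Finally, the date from which the 12 months are counted is not fixed. In section 2i the reference to the time of assessment is attached to the Kitbag-exposure criterion. If the 12 months were counted at T13, a child entering care in May 2021 could still have been Child in Need at the start. The model might then be estimable, but its reference would rest on very few children. In the numerical check, an assumed 1% in each of Child in Need and Child Protection restored estimability for all but the empty missing category.

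Choosing factor levels by outcome is often left to an analysis plan. Here, however, the Protocol itself fixes the reference and the interpretation, and for the SDQ that stated rule fails.

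**Conclusion.** Wrong as written, but minor. For the SDQ, the treatment coefficient and all four Child in Need-referenced interactions are not estimable, and the stated comparison with CINP children cannot be made. The accompanying readings of the treatment-by-Child-Protection and treatment-by-IFA/other terms fail with it.

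This rests on three assumptions: the section covers the SDQ, as its wording implies; the 12 months are counted at the SDQ date; and status is taken at May 2021. If the months are counted at T13, the reference cell is nearly empty rather than empty.

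It would be a mistake to infer that the main results are at risk. The primary-outcome version of the model has all its cells. In the main SDQ model the empty reference makes only the status indicators redundant with the intercept, so the SDQ treatment effect is untouched. The affected analysis is labelled exploratory.

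**What to change.** State that the interaction model with Child in Need as reference applies to the social care involvement outcome only. For the SDQ, use only the contrast the section already describes, fostering/kinship against IFA/other. Report the treatment effect with its interval in each of these two looked-after groups, and make no comparison with CINP or CPP children. The cost is one or two sentences in the Protocol or analysis plan, with no new data and no change to the primary or main secondary analyses.
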